#### 4.1.6 Prior Therapy

4.1.6.1 Patients must have fully recovered from the acute toxic effects of all prior anti-cancer therapy and must meet the following minimum duration from prior anti-cancer directed therapy prior to enrollment. If after the required timeframe, the defined eligibility criteria are met, e.g. blood count criteria, the patient is considered to have recovered adequately.

- a. Cytotoxic chemotherapy or other anti-cancer agents known to be myelosuppressive. See DVL homepage for commercial and Phase 1 investigational agent classifications. For agents not listed, the duration of this interval must be discussed with the study chair and the study-assigned Research Coordinator prior to enrollment.
  - i. At least 21 days after the last dose of cytotoxic or myelosuppressive chemotherapy (42 days if prior nitrosourea).
- b. Hematopoietic growth factors: At least 14 days after the last dose of a long-acting growth factor (e.g. pegfilgrastim) or 7 days for short-acting growth factor. For agents that have known adverse events occurring beyond 7 days after administration, this period must be extended beyond the time during which adverse events are known to occur. The duration of this interval must be discussed with the study chair.
- c. Anti-cancer agents not known to be myelosuppressive (e.g. not associated with reduced platelet or ANC counts): At least 7 days after the last dose of agent. See DVL homepage for commercial and Phase 1 investigational agent classifications. For agents not listed, the duration of this interval must be discussed with the study chair and the study-assigned Research Coordinator prior to enrollment.
- d. Interleukins, Interferons and Cytokines (other than Hematopoietic Growth Factors):  $\geq 21$  days after the completion of interleukins, interferon or cytokines (other than Hematopoietic Growth Factors)
- e. Antibodies:  $\geq 21$  days must have elapsed from infusion of last dose of antibody, and toxicity related to prior antibody therapy must be recovered to Grade  $\leq 1$ .
- f. XRT/External Beam Irradiation including Protons:  $\geq 14$  days after local XRT;  $\geq 150$  days after TBI, craniospinal XRT or if radiation to  $\geq 50\%$  of the pelvis;  $\geq 42$  days if other substantial BM radiation.
- g. Radiopharmaceutical therapy (e.g., radiolabeled antibody,  $^{131}\text{I}$ -MIBG):  $\geq 42$  days must have elapsed since systemically administered radiopharmaceutical therapy.
- h. Cellular Therapy:  $\geq 42$  days must have elapsed since the completion of any type of cellular therapy (e.g. modified T cells, NK cells, dendritic cells, etc.).
- i. Patients must not have received prior exposure to nivolumab. For patients enrolled in Parts C, D, and E patients must not have received prior nivolumab or ipilimumab.

#### 4.1.7 Organ Function Requirements

4.1.7.1 Adequate Bone Marrow Function Defined as:

- a. For patients with solid tumors without known bone marrow involvement:
  - Peripheral absolute neutrophil count (ANC)  $\geq 750/\text{mm}^3$
  - Platelet count  $\geq 75,000/\text{mm}^3$  (transfusion independent, defined as not receiving platelet transfusions for at least 7 days prior to enrollment)
- b. Patients with known bone marrow metastatic disease will be eligible for study provided they meet the blood counts in [4.1.7.1.a](#) (may receive transfusions provided they are not known to be refractory to red cell or platelet transfusions). These patients will not be evaluable for hematologic toxicity. At least 5 of every cohort of 6 patients with a solid tumor must be evaluable for hematologic toxicity, for Parts A and C. If dose-limiting hematologic toxicity is observed on either Part A or C, all subsequent patients enrolled must be evaluable for hematologic toxicity on that Part.

4.1.7.2 Adequate Renal Function Defined as:

- Creatinine clearance or radioisotope GFR  $\geq 70 \text{ ml/min/1.73 m}^2$  or
- A serum creatinine based on age/gender as follows:

Age	Maximum Serum Creatinine (mg/dL)	
	Male	Female
1 to < 2 years	0.6	0.6
2 to < 6 years	0.8	0.8
6 to < 10 years	1	1
10 to < 13 years	1.2	1.2
13 to < 16 years	1.5	1.4
$\geq 16$ years	1.7	1.4

The threshold creatinine values in this Table were derived from the Schwartz formula for estimating GFR (Schwartz et al. J. Peds, 106:522, 1985) utilizing child length and stature data published by the CDC.

4.1.7.3 Adequate Liver Function Defined as:

- Bilirubin (sum of conjugated + unconjugated)  $\leq 1.5 \times$  upper limit of normal (ULN) for age
- SGPT (ALT)  $\leq 135 \text{ U/L}$ . For the purpose of this study, the ULN for SGPT is 45 U/L.

4.1.7.4 Adequate Pulmonary Function Defined as:

- No evidence of dyspnea at rest, no exercise intolerance due to pulmonary insufficiency, and a pulse oximetry  $> 92\%$  while breathing room air.

4.1.7.5 Adequate Pancreatic Function Defined as:

- Serum lipase  $\leq \text{ULN}$  at baseline. Patients with glucose intolerance should be on a stable regimen and be monitored.

4.1.8 Informed Consent: All patients and/or their parents or legally authorized

representatives must sign a written informed consent. Assent, when appropriate, will be obtained according to institutional guidelines.

- 4.1.9 Tissue blocks or slides must be sent for all patients per [Section 8.6](#). If tissue blocks or slides are unavailable, the study chair must be notified prior to enrollment.

## 4.2 Exclusion Criteria

### 4.2.1 Pregnancy or Breast-Feeding

Pregnant or breast-feeding women will not be entered on this study due to risks of fetal and teratogenic adverse events as there is yet no available information regarding human fetal or teratogenic toxicities. Pregnancy tests must be obtained in girls who are post-menarchal. Women of childbearing potential (WOCBP) receiving nivolumab will be instructed to adhere to contraception for a period of 5 months after the last dose of nivolumab. Men receiving nivolumab and who are sexually active with WOCBP will be instructed to adhere to contraception for a period of 7 months after the last dose of nivolumab.

### 4.2.2 Concomitant Medications

4.2.2.1 Corticosteroids: Patients requiring daily systemic corticosteroids are not eligible. Patients must not have received systemic corticosteroids within 7 days prior to enrollment. If used to modify immune adverse events related to prior therapy,  $\geq 14$  days must have elapsed since last dose of corticosteroid. Note: Use of topical or inhaled corticosteroids will not render a patient ineligible.

4.2.2.2 Investigational Drugs: Patients who are currently receiving another investigational drug are not eligible.

4.2.2.3 Anti-cancer Agents: Patients who are currently receiving other anti-cancer agents are not eligible.

4.2.3 Patients with CNS tumors or known CNS metastases will be excluded from this trial due to concerns regarding pseudo-progression in the CNS. Patients with a history of CNS metastases that have been previously treated may enroll if sequential imaging shows not evidence for active disease. Patients with extra axial disease [e.g. skull (bone) metastasis that do not invade the dura] may enroll if there is no evidence for CNS edema associated with the lesion.

4.2.4 Patients with a history of any Grade autoimmune disorder are not eligible. Asymptomatic laboratory abnormalities (e.g. ANA, rheumatoid factor, altered thyroid function studies) will not render a patient ineligible in the absence of a diagnosis of an autoimmune disorder.

4.2.5 Patients with  $\geq$  Grade 2 hypothyroidism due to history of autoimmunity are not eligible. Note: Hypothyroidism due to previous irradiation or thyroidectomy will not impact eligibility.

4.2.6 Infection: Patients who have an uncontrolled infection are not eligible.

4.2.7 Patients with a history of CHF or are at risk because of underlying cardiovascular disease or exposure to cardiotoxic drugs must have adequate cardiac function as clinically indicated:

- QTC  $\leq$  480 msec;
- Shortening fraction of  $\geq$  27% by echocardiogram or ejection fraction of  $\geq$  50% by gated radionuclide study

- 4.2.8 Patients with known HIV or hepatitis B or C are excluded.
- 4.2.9 Patients who have received prior solid organ transplantation are not eligible.
- 4.2.10 Patient who have received allotransplantation are not eligible.
- 4.2.11 Patients who in the opinion of the investigator may not be able to comply with the safety monitoring requirements of the study are not eligible.
- 4.2.12 Patients who have received prior anti-PD1 directed therapy (mAb or small molecule) are not eligible.
- 4.2.13 Parts C, D, and E: Patients who have received prior ipilimumab are not eligible.

## 5.0 TREATMENT PROGRAM

### 5.1 Overview of Treatment Plan

This trial will consist of Parts A-E as described below. Once the dose-escalation portion of Part A is completed, cohorts that are open concurrently for eligible patients (including Parts B and C and potential PK expansion cohorts) may be selected at the treating physician's discretion pending slot availability. Part B will be completed for all cohorts after the initial stage of Simon's optimal two-stage design ([Section 11.4](#)). Upon opening Part E to accrual, no additional patients will be enrolled to Part D.

Once enrolled, patients continue on the part of the study assigned at enrollment until they meet criteria in [Section 10.1](#) or [Section 10.2](#).

Pre-medication is not required as infusional reactions are rare, but anaphylactic precautions should be observed during each infusion of nivolumab. If  $\geq$  Grade 2 infusional reaction occurs, the infusion should be stopped and supportive care given as per institutional guidelines. See [Section 6.3](#) for management and dose modification guidelines for infusional reactions. Investigators are advised to monitor for fever, chills, shakes, itching, rash, hypertension or hypotension, or difficulty breathing during and immediately after administration of nivolumab.

Drug doses should be adjusted based on the patient's actual weight in kilograms measured within 7 days prior to the beginning of each cycle.

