### 5.1.2 Part B (COMPLETED)

Part B will evaluate the activity of nivolumab at its RP2D in expanded cohorts for patients with neuroblastoma, osteosarcoma, rhabdomyosarcoma, Ewing sarcoma, Hodgkin lymphoma, non-Hodgkin lymphoma. In the melanoma cohort (Part B7), toxicities and disease response will be reported descriptively within the confines of a Phase 1/2 study.

Dose Level	Nivolumab (mg/kg) IV over 60 min.	Day(s) of Administration
1	3	1, 15

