#### 5.1.4 Part D (COMPLETED)

If criteria for accrual to Part D are met, the combination of nivolumab and ipilimumab will be administered every 3 weeks X 4 followed by nivolumab given every 2 weeks until off protocol criteria in [Section 10.1](#) are met. **Note that cycle length is 21 days for the first 4 cycles of Part D, whereas reverts to 28 days for subsequent cycles which comprises two doses of nivolumab, and is the same regimen used in Part A and B.**

Dose Level	Cycles 1-4	Cycles 5+
1	Nivolumab (IV over 60 min) 3 mg/kg on Day 1  Ipilimumab (IV over 90 min) 1 mg/kg on Day 1	Nivolumab (IV over 60 min) 3 mg/kg on Days 1 and 15

Infusion of ipilimumab (over 90 minutes) should be initiated no sooner than 30 minutes after completion of the nivolumab infusion.

Vital signs (temperature, pulse, blood pressure and respirations) will be monitored closely baseline then every 15 minutes x 2, then every 30 minutes x 3 beginning at the initiation of administration of ipilimumab infusion. Patients who develop symptoms or signs of hypotension ( $\geq 25\%$  decrease in systolic or diastolic blood pressures from baseline) that are temporally related to ipilimumab infusion will receive additional IV fluids as appropriate until the signs and symptoms resolve. During cycle 1, patients must remain for observation for a total of 6 hours following completion of ipilimumab. The post administration observation period may be extended to 24 hours and the patient admitted if clinically indicated. If the patient tolerates the first infusion of ipilimumab without incident, the observation period may be reduced to 90 minutes following completion of the drug infusion with subsequent cycles. Any patient who develops Grade 3 or 4 anaphylaxis felt to be primarily related to administration of ipilimumab will be removed from protocol therapy.

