A minimum of 10 evaluable patients per disease group will be enrolled in Parts B1-B6 and B8 and Parts D1-6. A maximum 22 per disease group will be enrolled in these cohorts. A non-statistical access cohort for the rare diagnosis of melanoma (Part B7) will remain open to enrollment until Parts B1-B6, B8 and Parts D1-6 are complete. If at any time after enrollment of three patients, cycle 1 DLT occurs in  $\geq 33\%$  in the melanoma cohort, enrollment to that cohort will be closed. There will be no required minimum or maximum accrual limits for Part B7; however, given the accrual rate of 3-4 patients/year a minimum of 0 evaluable patients and a maximum of 16 patients is anticipated to enroll in this disease group assuming the maximum study duration of 4 years. The maximum enrollment assumes a 10% inevaluable rate. Therefore, a minimum of 60 patients and a maximum of 170 patients will be enrolled in Part B. A maximum of 110 patients will be enrolled in Part D.

As cohort D5 investigates the combination of nivolumab and ipilimumab in patients who may be post-allogeneic BMT, if at any time after 3 enrollments, acute or chronic GVHD requiring systemic immunosuppression occurs in  $\geq 33\%$  of patients, the strata will be closed to accrual.

A minimum of 6 children  $< 12$  years of age and at least 6 children  $\geq 12$  years of age will be evaluated for tolerability and systemic exposure of single agent nivolumab RP2D in Parts A and B. If less than 6 patients  $< 12$  years of age are enrolled upon completion of accrual to Part B, additional children (any histology) will be added to Part A studied to reach the 6 patient minimum.

Update: As of Amendment #8 a total of 132 patients have been enrolled:

Part A: 13 patients

Part B: B1: 10 patients

B2: 10 patients

B3: 11 patients

B4: 10 patients

B5: 12 patients

B6: 10 patients

B7: 1 patient

B8: 8 patients

Part C: 18 patients

Part D: D2: 10 patients

D3: 10 patients

D4: 9 patients

A total 132 patients have enrolled into ADVL1412 to date. A minimum of 3 evaluable patients will be enrolled in Part E, and a maximum of 23 patients will be enrolled overall. The maximum enrollment assumes a 10% inevaluable rate, and this part of the study is anticipated to be completed within 2-23 months. Therefore, the maximum number of patients for the entire study is expected to be 155 with amendment 8, and this entire protocol will have been completed within 5.5 years.

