### 11.4 Phase 2 Evaluation of Nivolumab (for Part B):

#### Study Design

The best response of disease to nivolumab will be examined separately for each of the tumor strata: neuroblastoma, osteosarcoma, rhabdomyosarcoma, ewing sarcoma, Hodgkin lymphoma, and non-Hodgkin lymphoma with the goal of enrolling at least evaluable 10 patients per tumor type. Given the activity seen in adult patients with melanoma, an additional non-statistical cohort for patients with unresectable, metastatic, relapsed or refractory melanoma will be open to accrual as Part B7 to preliminarily define the antitumor effects of nivolumab within the confines of a phase 1/2 study and will remain open for enrollment until Parts B1-B6, B8 are complete. Given the rarity of the disease in the pediatric population the study will not remain open to complete this cohort if all other strata have completed accrual. If at any time after enrollment of three patients, cycle 1 DLT occurs in  $\geq$

33% in the melanoma cohort, enrollment to that cohort will be closed. If at least 12 patients are treated at Part B7, evaluation of accrual rate and toxicities may be discussed with the sponsor to determine if any changes in study design are required. The following Simon's optimal two stage design will be used for Parts B1-B6, B8.

	Cumulative Number of Responses	Decision
Stage 1: Enter 10 patients	0	Terminate the stratum: agent ineffective
	1 or more	Inconclusive result, continue stratum (proceed to stage 2)
Stage 2: Enter 10 additional patients	2 or less	Terminate the stratum: agent ineffective
	3 or more	Terminate the stratum: agent effective

In the event that a cohort in a given disease group in Part B is completed after Stage 1 because no responses are observed, a cohort in the same disease group will open to up to 10 evaluable patients in Part D, at the RP2D of nivolumab in combination with ipilimumab as determined in Part C: 3 mg/kg nivolumab and 1 mg/kg ipilimumab (See [Section 11.6](#)).

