Nivolumab will not be considered of sufficient interest for further evaluation in a disease category if the true response rate is 5% and of sufficient activity if the true response rate is 25%. If nivolumab has a true response rate of 5%, the rule described above will identify it of sufficient activity for further study with probability 0.07 (type I error), and the trial will have an expected sample size of 14 with 60% probability of early termination. If nivolumab has a true response rate of 25%, the rule described above will identify it of sufficient activity for further study with probability 0.88 (power against the alternative hypothesis  $P = 0.25$ ).

Children with a target diagnosis and measurable or MIBG evaluable disease who are enrolled on Part A and receive the RP2D will be considered evaluable for disease response in Part B.

If cycle 1 DLT occurs in  $\geq 33\%$  of evaluable patients in a cohort of Part B with at least 3 evaluable patients, the maximum tolerated dose will have been exceeded in this tumor type and the cohort will be closed to further enrollment.

Response in all patients with solid tumors will be determined according to RECIST as defined in the protocol as either complete response (CR), partial response (PR), stable disease (SD) or progressive disease (PD), or as described in [Section 12.0](#) for other categories of responses assessment, and reported as final results. A report on the efficacy assessment will be posted on the completed disease stratum as part of the semi-annual study committee meeting book report.

Method of Analysis

Response criteria are described in [Section 12.0](#). Response rates will be calculated separately for each of the tumor strata as the percent of patients whose best response is a CR or PR and confidence intervals will be constructed according to the method of Chang. A responder is defined as a patient who achieves a best confirmed response (as defined in [Section 12.6](#)) of PR or CR on the study and includes pseudo-progressive disease. Response is defined relative to baseline disease.

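### The 0.07 type I error and 0.88 power stated for Parts B and D belong to a 10+10 design whose stage 2 will not run, and a stratum closed with 1 or 2 confirmed responses has no planned conclusion

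*Combined protocol and SAP*

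**What the plan says.** **The rule.** Section 11.4 (Part B) and Section 11.6.1 (Part D) print the same table. With 0 responses in the first 10 patients the stratum stops as ineffective. With 1 or more the table reads "Inconclusive result, continue stratum (proceed to stage 2"). After 10 further patients, 2 or fewer cumulative responses means ineffective and 3 or more means effective. The effective outcome appears only in the stage 2 rows. For response rates of 5% and 25%, both sections give a type I error of 0.07 and say the rule will "identify it of sufficient activity for further study with probability 0.88 (power against the alternative hypothesis" of 25%).

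**The closures.** Section 5.1 says "Part B will be completed for all cohorts after the initial stage of" the two-stage design, with no exception for cohorts that showed responses. It adds: "Upon opening Part E to accrual, no additional patients will be enrolled to Part D". Section 2.11 closes Part D by amendment, and the headings of Sections 5.1.2 and 5.1.4 mark Parts B and D as completed. Section 11.1 says "the maximum number of patients for the entire study is expected to be 155 with amendment 8".

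**What is known about responses.**
- Section 2.5 reports preliminary data with no objective responses in osteosarcoma, Ewing sarcoma and rhabdomyosarcoma in Part B, 10 patients each.
- Section 2.4 reports one partial response in rhabdomyosarcoma at the Part D dose. Section 11.1 lists 10 patients in D3.
- Section 2.10 plans to close the Hodgkin stratum (B5) because activity seems clear, partly on data from outside this trial, while formal response evaluation was still under way.
- Section 11.2.3 requires central confirmation before a response counts in the rule.

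**The interval.** Both sections specify the method of Chang, cited to a paper on intervals after a group sequential phase II trial (reference 57).

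**The concern.** Antitumor effect in Parts B and D is among the primary aims in Section 1.1, and Sections 11.4 and 11.6.1 still govern how it is reported. A reader would credit every stratum with a decision rule of power 0.88. For a stratum that showed 1 or 2 responses, that rule can no longer be completed: the table sends it to a stage 2 that will not run, and no other conclusion is provided. Without a written rule, the label would be chosen with the responses already known. The interval is unsettled for the same reason, since closing at stage 1 with responses is not one of the design's stopping outcomes.

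**Working it through.** **Inputs.** Stage 1 size 10, stop at 0; total 20, effective at 3 or more; response rates p = 0.05 and p = 0.25 (Sections 11.4 and 11.6.1). Enrolment counts are from Section 11.1.

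**1. The plan's own figures.** With X1 and X2 independent Bin(10, p),

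P(effective) = P(X1=1)·P(X2≥2) + P(X1=2)·P(X2≥1) + P(X1≥3).

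- p = 0.05: 0.3151 × 0.0861 + 0.0746 × 0.4013 + 0.0115 = 0.0686.
- p = 0.25: 0.1877 × 0.7560 + 0.2816 × 0.9437 + 0.4744 = 0.8820.
- Early stop at p = 0.05: 0.95^10 = 0.5987. Expected size: 10 + 10 × (1 − 0.5987) = 14.0.

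The stated 0.07, 0.88, 60% and 14 all reproduce.

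**2. Is there room for stage 2?** Part B: 10 + 10 + 11 + 10 + 12 + 10 + 1 + 8 = 72. Part D: 10 + 10 + 9 = 29. With 13 in Part A and 18 in Part C, 13 + 72 + 18 + 29 = 132. Adding 23 for Part E gives 155, the stated maximum. Nothing is left for stage 2 of Part B or D.

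**3. Outcomes when a stratum ends at 10 evaluable patients.**

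| Responses in 10 | p = 0.05 | p = 0.25 | Status under the printed table |
|---|---|---|---|
| 0 | 0.599 | 0.056 | Planned futility stop |
| 1 or 2 | 0.390 | 0.469 | Sent to stage 2; no conclusion available |
| 3 or more | 0.0115 | 0.474 | Cumulative threshold already met |

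**4. Could any 10-patient cutoff carry the stated figures?**

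| Cutoff in 10 | Type I error | Power at 25% |
|---|---|---|
| 1 or more | 0.401 | 0.944 |
| 2 or more | 0.086 | 0.756 |
| 3 or more | 0.0115 | 0.474 |

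None gives 0.07 and 0.88. These rows are illustrative; the plan specifies no 10-patient test.

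**5. How open is D3?** Take its one response as confirmed and N as 10. A full stage 2 would have needed 2 or more further responses: P(X2≥2) = 0.086 at a 5% rate and 0.756 at 25%. The exact (Clopper-Pearson) 95% interval for 1/10 is 0.3% to 44.5%, which includes both design rates.

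**The case against.** The stated probabilities are properties of the printed rule, and they are right. Neither section claims them as achieved power after closure, and the closures are disclosed. Parts B and D are no longer enrolling, so no accrual decision depends on their rule, and Part E has its own 10+10 rule in Section 11.7.1, which this point does not touch. All of this stands. What is missing is a statement of what the closures do to the rule, and it still matters because those sections govern final reporting.

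A reader might infer several stronger claims that the documents do not support:

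- *Every stratum with 1 or more responses is stranded* (0.401 at 5%, 0.944 at 25%). The table counts cumulative responses, so 3 or more in stage 1 cannot be reversed. The gap is 1 or 2 responses only.
- *The Hodgkin stratum B5 is a further case.* Section 2.10 says several patients had tumor shrinkage but gives no count of confirmed responses. B5 may already have 3 or more.
- *The plan's real power is 0.474.* That figure belongs to a test of 3 or more in 10 that the plan never specified. It also counts 1 or 2 responses as failures, which the table does not.
- *The Chang interval is invalid here.* The documents give only the reference's title and do not show that the method fails for such a closure. The supported point is that the plan does not say how the interval is then formed.
- *The sentence "A maximum 22 per disease group will be enrolled in these cohorts" contradicts the 155 total.* The Amendment 8 update in the same section overtakes it.

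The evidence is weaker for Part D. Only Part B is said to end after stage 1; for Part D the absence of stage 2 follows from its closure and the counts. Those counts are not fully consistent: Section 2.9 has 46 patients treated at 3 mg/kg plus 1 mg/kg by April 2018, while Section 11.1 allows at most 18 − 5 + 29 = 42 (the 5 being the evaluable patients at Part C dose level 1). The difference of 4 is smaller than one 10-patient stage 2.

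**Conclusion.** The concern holds in a limited form. The figures 0.07 and 0.88 are correct for the 10+10 design but do not describe strata of Parts B and D closed at about 10 patients. Strata with 0 of 10 followed the plan, and strata with 3 or more confirmed responses have met its threshold. A stratum with 1 or 2 confirmed responses has no planned conclusion; the chance of landing there is 0.390 at a 5% rate and 0.469 at 25%.

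These probabilities assume exactly 10 evaluable patients. The actual number may differ: B8 is listed with 8 and D4 with 9, and Sections 11.4 and 11.6.1 let eligible Part A and Part C patients count toward Parts B and D. D3 is the one documented likely case, subject to its evaluable number and to central confirmation of its response. The documents give no response results for B1, B6 or B8. The effect is on the reported conclusion for a primary aim, not on patient safety, and the plan should be corrected.

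**What to change.** In Sections 11.4 and 11.6.1:

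1. State that accrual to Parts B and D ended without stage 2 (the sponsor should confirm this for Part D), and that 0.07 and 0.88 apply to the planned 10+10 design only, not to strata closed early. Mark any 10-patient figures, such as 0.0115 and 0.474 for 3 or more of 10, as illustrative and not as a prespecified test.
2. Name the label for each stage 1 outcome. 0 responses in 10 evaluable patients is the planned futility stop. 1 or 2 centrally confirmed responses is reported as inconclusive, closed before stage 2, and neither effective nor ineffective. 3 or more is reported as having met the cumulative threshold.
3. For strata closed at stage 1 with 1 or more responses, say how the interval is formed on the actual evaluable number. A descriptive exact Clopper-Pearson interval would serve (1/10: 0.3% to 44.5%; 2/10: 2.5% to 55.6%; 3/10: 6.7% to 65.2%).

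This costs one short paragraph in each section and needs no new data. The downside is that the stated power for Parts B and D becomes less favourable and some strata are labelled inconclusive.
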